#### 5.1.1.6 Immunogenicity

In a Phase 1 single-dose study (SA-001JP) of satralizumab in healthy Japanese and Caucasian adult male volunteers, ADA were detected in 39 of the 72 patients who received satralizumab. Most of ADAs were characterized as neutralizing antibody. In a Phase 1 multiple dose study of satralizumab (SA-105JP) in patients with RA, ADA were detected in 2 of the 33 patients who received satralizumab. These ADAs were also characterized as neutralizing antibody, and in these 2 patients, elevation of serum level of satralizumab was not observed.

*In the double-blind periods of the Phase 3 studies, ADAs were observed in 41% (Study BN40898) and 71% (Study BN40900) of patients receiving satralizumab. Exposure was lower in ADA positive patients; however, there was no impact of*

*ADAs on safety and no clear impact on efficacy or pharmacodynamic markers indicative of target engagement.*

#### **5.1.1.7 Serious Hypersensitivity Reactions**

Anaphylaxis and serious hypersensitivity reactions have not been reported in clinical trials with satralizumab treatment; however, anaphylaxis and hypersensitivity reactions are considered a potential risk with all biologic medications, including satralizumab.

Patients with a history of a severe allergic reaction to a biologic agent are excluded from study participation.

The symptoms/signs of hypersensitivity include, but are not limited to, blood pressure decrease, dyspnea, loss of consciousness, dizziness, queasiness, vomiting, itchiness, flushing, etc. A decision to continue/discontinue treatment with satralizumab should be made taking into account the risks and benefits if any of these events are observed.

- *Up to Week 48 in the OLE period of the study:*
  - The SC injections should be administered under close supervision in a setting where medications (e.g. corticosteroid, antihistamine and epinephrine) and resuscitation facilities are available
  - Patients should stay in the clinic/hospital at least 1 hour after study drug administration in order to receive medication immediately if anaphylaxis occurs.
- Patients should be instructed to seek medical attention if they experience symptoms of hypersensitivity reaction outside of the clinic.
- If an anaphylactic reaction or other serious hypersensitivity reaction occurs, satralizumab should be discontinued.
- *Administration of satralizumab prefilled syringes outside of the study site might be allowed (see Section 4.3.2.2) if the investigator determines that it is appropriate. Patients/caregivers should be instructed to recognize the signs and symptoms of hypersensitivity reactions and instructed to seek immediate medical attention if the patient develops symptoms of serious allergic reactions. Patients/caregivers should confirm with the investigator whether treatment with satralizumab may be continued.*

#### **5.1.1.8 CYP450 Enzyme Normalization**

Drug interaction studies have not been conducted with satralizumab. In patients with RA who were administered tocilizumab, increased expression of CYP3A4, CYP2C19 and CYP2D6 has been suggested. Reports have suggested that overproduction of IL-6 in patients with inflammatory response inhibits the expression of CYPs. Satralizumab administration may normalize CYP expression and the beneficial effects of concomitant drugs may decrease as the inflammatory reaction improves.

Patients taking medicinal products *that* are individually adjusted and are metabolized via CYP450 3A4, 1A2, 2C9 or 2C19 should be monitored as doses may need to be *modified*.

#### **5.1.1.9 Complications of Diverticulitis**

Gastrointestinal perforations have not been reported in clinical trials with satralizumab treatment.

*To date*, gastrointestinal perforations have been reported rarely in patients administered tocilizumab. Although it is unknown whether gastrointestinal perforations are associated with IL-6 inhibition, satralizumab may suppress the acute symptoms (abdominal pain, pyrexia etc.) associated with diverticulitis, etc., causing delayed diagnosis and progression to perforation.

In this *study*, a history of active diverticulitis may preclude patient from participation.

- Patients presenting with symptoms potentially indicative of complicated diverticulitis, such as abdominal pain, should be evaluated (X-ray, computerized tomography [CT] scan, etc.) promptly for early identification of gastrointestinal perforation and appropriate measures taken.
- Patients should be made aware of the symptomatology potentially indicative of complicated diverticular disease, and they should be instructed to alert their healthcare provider as soon as possible if these symptoms arise.
- In patients who receive corticosteroids and/or non-steroidal anti-inflammatory drugs, prophylactic treatment with proton pump inhibitors or H2 blocker should be considered.

#### **5.1.1.10 Malignancies**

*No increased risk of malignancies has been observed* in clinical trials with satralizumab treatment.

Although malignancies have been reported in patients given tocilizumab, there have been no report to date that tocilizumab appreciably increases the occurrence of malignancies.

All patients with history of malignancy within the last 5 years, including solid tumors, hematologic malignancies and in situ carcinoma (except basal cell and squamous cell carcinomas of the skin, or in situ carcinoma of the cervix uteri that have been completely excised and cured) will be excluded from this study.

Satralizumab should be discontinued in patients with malignancies (with the exception of local basal or squamous cell carcinoma of the skin that is completely excised with free margins)

#### **5.1.1.11 Demyelinating Disorders**

Demyelination-related diseases have not been reported in clinical trials with satralizumab treatment.

The impact of treatment with tocilizumab on demyelinating disorders is not known, but MS and chronic inflammatory demyelinating polyneuropathy were reported rarely in RA clinical studies. PML has not been reported.

Patients with evidence of other demyelinating disease or PML will be excluded from this study.

If symptoms suggestive of a demyelination-related disease are observed, differential diagnosis of the cause should be performed.

#### **5.1.1.12 Concomitant Medications**

Patients should also be informed of the risks associated with taking corticosteroids, azathioprine or mycophenolate mofetil. Below are listed specific major risks that patients need to be aware of:

- Corticosteroids can cause immunosuppression, hypertension, diabetes mellitus, cataracts, glaucoma, bruising, thinning of the skin, weight gain, psychological changes, osteoporosis, accelerated atherosclerosis, increased risk of gastrointestinal bleeding, aseptic necrosis of bone and adrenal insufficiency. Although rare, steroid-induced hypersensitivity reactions do occur. They range from minor rashes to the more serious cardiovascular collapse. For additional safety data, refer to the local prescribing information.
- No evidence available at the time of approval of this study protocol indicated that special warnings or precautions were appropriate, other than those noted in the Investigator's Brochure.

## 5.2 SAFETY PARAMETERS AND DEFINITIONS

Safety assessments will consist of monitoring and recording AEs, including SAEs, AESIs and selected AEs; measurement of protocol-specified safety laboratory assessments; measurement of protocol-specified vital signs; and other protocol-specified tests that are deemed critical to the safety evaluation of the study.

Certain types of events require immediate reporting to the Sponsor, as outlined in Section 5.4.

### 5.2.1 Adverse Events

According to the ICH guideline for GCP, an AE is any untoward medical occurrence in a clinical investigation subject administered a pharmaceutical product, regardless of causal attribution. An AE can therefore be any of the following:

- Any unfavorable and unintended sign (including an abnormal laboratory finding), symptom, or disease temporally associated with the use of a medicinal product, whether or not considered related to the medicinal product
- Any new disease or exacerbation of an existing disease (a worsening in the character, frequency, or severity of a known condition), except as described in Section 5.3.5.9
- Recurrence of an intermittent medical condition (e.g., headache) not present at baseline
- Any deterioration in a laboratory value or other clinical test (e.g., ECG, X-ray) that is associated with symptoms or leads to a change in study drug or concomitant treatment or discontinuation from study drug
- Adverse events that are related to a protocol-mandated intervention, including those that occur prior to assignment of study drug (e.g., invasive screening procedures such as biopsies)

New or worsening neurological symptoms considered NMO-related are not AEs. Clinical relapse will be recorded only on a pre-specified eCRF “NMO relapse” form.

### 5.2.2 Serious Adverse Events (Immediately Reportable to the Sponsor)

An SAE is any AE that meets any of the following criteria:

- Fatal (i.e., the AE actually causes or leads to death)
- Life threatening (i.e., the AE, in the view of the Investigator, places the patient at immediate risk of death)

This does not include any AE that had it occurred in a more severe form or was allowed to continue might have caused death

- Requires or prolongs inpatient hospitalization (see Section 5.3.5.10)
- Results in persistent or significant disability/incapacity (i.e., the AE results in substantial disruption of the patient's ability to conduct normal life functions)
- Congenital anomaly/birth defect in a neonate/infant born to a mother exposed to study drug
- Significant medical event in the Investigator's judgment (e.g., may jeopardize the patient or may require medical/surgical intervention to prevent one of the outcomes listed above)

The exception to this definition of an SAE is in the rare event that a patient is hospitalized following an NMO relapse, as long as the reason for hospitalization is to receive standard treatment with rescue therapy for clinical relapse.

The terms "severe" and "serious" are not synonymous. Severity refers to the intensity of an AE (rated as mild, moderate, or severe] criteria; see Section 5.3.3); the event itself may be of relatively minor medical significance (such as severe headache without any further findings).

Severity and seriousness need to be independently assessed for each AE recorded on the eCRF.

Serious adverse events are required to be reported by the Investigator to the Sponsor within 24 hours after learning of the event (see Section 5.4.2 for reporting instructions).

### **5.2.3 Non-serious Adverse Events of Special Interest (Immediately Reportable to the Sponsor)**

Non-serious AESIs are required to be reported by the Investigator to the Sponsor within 24 hours after learning of the event (see Section 5.4.2 for reporting instructions). Non-serious AEs of Special Interest for this study include the following:

- Cases of an elevated ALT or AST in combination with either an elevated bilirubin or clinical jaundice, as defined in Section 5.3.5.6
- Suspected transmission of an infectious agent by the study drug.

### **5.2.4 Selected Adverse Events**

Additional data will be collected for the following selected AEs. The data should be recorded in the eCRF on the AE page and on the special form for that particular AE.

- Infections that require treatments with IV antibiotics, antifungals, or antivirals\*
- Opportunistic infections that require treatments with oral antibiotics, antifungals, or antivirals\*

- Injection-related reaction (IRR; an AE which occurs within 24 hours after study drug injection except where the event is not considered an allergic reaction)†

\* Selected AEs will be reviewed by Sponsor and Medical Monitor to identify infections requiring IV treatment and opportunistic infections that require treatments. AE listings will also be searched to identify any infections requiring IV treatment/opportunistic infections which have not been reported as Selected AEs.

† Each IRR will be reviewed by the Medical Monitor to assess the risk of anaphylaxis.

### **5.3 METHODS AND TIMING FOR CAPTURING AND ASSESSING SAFETY PARAMETERS**

The Investigator is responsible for ensuring that all AEs (see Section 5.2.1) are recorded on the Adverse Event pages of the eCRF and reported to the Sponsor in accordance with instructions provided in this section and in Sections 5.4–5.6. The Investigator is also responsible for reporting medical device complaints (see Section 5.4.4).

For each AE recorded on the Adverse Event pages in the eCRF, the Investigator will make an assessment of seriousness (see Section 5.2.2 for seriousness criteria), severity (see Section 5.3.3), and causality (see Section 5.3.4).

#### **5.3.1 Adverse Event Reporting Period**

Investigators will seek information on AEs at each patient contact. All AEs, whether reported by the patient or noted by study personnel, will be recorded in the patient's medical record and on the Adverse Event pages of the eCRF.

After informed consent has been obtained but prior to initiation of study drug, only SAEs caused by a protocol-mandated intervention should be reported (e.g., SAEs related to invasive procedures of the protocol). These SAEs will be recorded in the Drug Safety database and not on the Adverse Event eCRF.

After initiation of study drug, all AEs, regardless of relationship to study drug, will be reported on the eCRF until the Withdrawal Visit or Last Observation (12 weeks after the last dose of study drug). After this period, investigators should report any deaths, SAEs, or other AEs of concern that are believed to be related to prior treatment with study drug (see Section 5.6).

### 5.3.2 Eliciting Adverse Event Information

A consistent methodology of non-directive questioning should be adopted for eliciting AE information at all patient evaluation time points. Examples of non-directive questions include the following:

“How have you felt since your last clinic visit?”

“Have you had any new or changed health problems since you were last here?”

### 5.3.3 Assessment of Severity of Adverse Events

Table 5 provides guidance for assessing AE severity.

**Table 5: Adverse Event Severity Grading**

Severity	Description
Mild	Discomfort noticed, but no disruption of normal daily activity
Moderate	Discomfort sufficient to reduce or affect normal daily activity
Severe	Incapacitating with inability to work or to perform normal daily activity

Note: Regardless of severity, some events may also meet seriousness criteria. Refer to definition of a SAE (see Section 5.2.2).

### 5.3.4 Assessment of Causality of Adverse Events

Investigators should use their knowledge of the patient, the circumstances surrounding the event, and an evaluation of any potential alternative causes to determine whether or not an AE is considered to be related to the study drug, indicating "yes" or "no" accordingly on the AE page of the eCRF. The following guidance should be taken into consideration:

- Temporal relationship of event onset to the initiation of study drug
- Course of the event, considering especially the effects of dose reduction, discontinuation of study drug, or reintroduction of study drug (where applicable)
- Known association of the event with the study drug or with similar treatments
- Known association of the event with the disease under study
- Presence of risk factors in the patient or use of concomitant medications known to increase the occurrence of the event
- Presence of non-treatment-related factors that are known to be associated with the occurrence of the event.

### **5.3.5 Procedures for Recording Adverse Events**

Investigators should use correct medical terminology/concepts when recording AEs on the Adverse Event page of the eCRF. Colloquialisms and abbreviations should be avoided.

Only one AE term should be recorded in the event field on the Adverse Event page of the eCRF.

#### **5.3.5.1 Diagnosis versus Signs and Symptoms**

##### *Injection-Related Reactions*

Injection-related reaction is defined as the event that occurs within 24 hours after study drug injection. An IRR should be recorded on the IRR page of the eCRF as "injection-related reaction", and individual signs and symptoms should also be captured on the IRR page of the eCRF.

But exceptive conditions are as follows:

- Anaphylaxis or anaphylactic shock:  
If the event is judged as anaphylaxis or anaphylactic shock by Investigator's discretion, it will be recorded on the Adverse Event page of the eCRF.
- Obviously not allergic reaction (e.g., infection):  
If the event is judged as not allergic reaction, it will be recorded on the Adverse Event page of the eCRF.

##### *Other Adverse Events*

For AEs other than IRRs, a diagnosis (if known) should be recorded on the Adverse Event page of the eCRF rather than individual signs and symptoms (e.g., record only liver failure or hepatitis rather than jaundice, asterixis, and elevated transaminases). However, if a constellation of signs and/or symptoms cannot be medically characterized as a single diagnosis or syndrome at the time of reporting, each individual event should be recorded on the Adverse Event page of the eCRF. If a diagnosis is subsequently established, all previously reported AEs based on signs and symptoms should be nullified and replaced by one AE report based on the single diagnosis, with a starting date that corresponds to the starting date of the first symptom of the eventual diagnosis.

#### **5.3.5.2 Adverse Events Occurring Secondary to Other Events**

In general, AEs occurring secondary to other events (e.g., cascade events or clinical sequelae) should be identified by their primary cause, with the exception of severe or serious secondary events. However, medically significant AEs occurring secondary to

an initiating event that are separated in time should be recorded as independent events on the Adverse Event page of the eCRF. For example:

- If vomiting results in mild dehydration with no additional treatment in a healthy adult, only vomiting should be reported on the eCRF.
- If vomiting results in severe dehydration, both events should be reported separately on the eCRF.
- If a severe gastrointestinal hemorrhage leads to renal failure, both events should be reported separately on the eCRF.
- If dizziness leads to a fall and subsequent fracture, all three events should be reported separately on the eCRF.
- If neutropenia is accompanied by an infection, both events should be reported separately on the eCRF.

All AEs should be recorded separately on the Adverse Event page of the eCRF if it is unclear as to whether the events are associated.

#### **5.3.5.3 Persistent or Recurrent Adverse Events**

A persistent AE is one that extends continuously, without resolution, between patient evaluation time points. Such events should only be recorded once on the Adverse Event page of the eCRF. The initial severity of the event should be recorded, and the severity should be updated to reflect the most extreme severity any time the event worsens. If the event becomes serious, the Adverse Event page of the eCRF should be updated to reflect this.

A recurrent AE is one that resolves between patient evaluation time points and subsequently recurs. Each recurrence of an AE should be recorded separately on the Adverse Event page of the eCRF.

#### **5.3.5.4 Abnormal Laboratory Values**

Not every laboratory abnormality qualifies as an AE. A laboratory test result should be reported as an AE if it meets any of the following criteria:

- Accompanied by clinical symptoms
- Results in a change in study drug (e.g., dosage modification, treatment interruption, or treatment discontinuation)
- Results in a medical intervention (e.g., potassium supplementation for hypokalemia) or a change in concomitant therapy
- Clinically significant in the Investigator's judgment

It is the Investigator's responsibility to review all laboratory findings. Medical and scientific judgment should be exercised in deciding whether an isolated laboratory abnormality should be classified as an AE.

If a clinically significant laboratory abnormality is a sign of a disease or syndrome (e.g., alkaline phosphatase and bilirubin 5 times the ULN associated with cholecystitis), only the diagnosis (i.e., cholecystitis) should be recorded on the Adverse Event page of the eCRF.

If a clinically significant laboratory abnormality cannot be related to a disease or syndrome, the abnormality itself should be recorded on the Adverse Event page of the eCRF, along with a descriptor indicating if the test result is above or below the normal range (e.g., "elevated potassium" as opposed to "abnormal potassium"). If the laboratory abnormality can be characterized by a precise clinical term per standard definitions, the clinical term should be recorded as the AE. For example, an elevated serum potassium level of 7.0 mEq/L should be recorded as "hyperkalemia."

Observations of the same clinically significant laboratory abnormality from visit to visit should not be repeatedly recorded on the Adverse Event page of the eCRF, unless the etiology or severity changes. The initial severity of the event should be recorded, and the severity or seriousness should be updated any time the event worsens or improves.

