#### **5.3.5.5 Abnormal Vital Sign Values**

Not every vital sign abnormality qualifies as an AE. A vital sign result should be reported as an AE if it meets any of the following criteria:

- Accompanied by clinical symptoms
- Results in a change in study drug (e.g., dosage modification, treatment interruption, or treatment discontinuation)
- Results in a medical intervention or a change in concomitant therapy
- Clinically significant in the Investigator's judgment

It is the Investigator's responsibility to review all vital sign findings. Medical and scientific judgment should be exercised in deciding whether an isolated vital sign abnormality should be classified as an AE.

If a clinically significant vital sign abnormality is a sign of a disease or syndrome (e.g., high blood pressure), only the diagnosis (i.e., hypertension) should be recorded on the Adverse Event page of the eCRF.

Observations of the same clinically significant vital sign abnormality from visit to visit should not be repeatedly recorded on the Adverse Event page of the eCRF, unless the etiology or severity changes. The initial severity of the event should be recorded, and the severity or seriousness should be updated any time the event worsens or improves.

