## **6.6 SAFETY ANALYSES**

All safety analyses will be performed on the SAF. Safety variables to be assessed are AEs, AESIs, SAEs, selected AEs, injection site reactions, patient withdrawals due to AEs, change in 12-lead ECGs, measurements of laboratory parameters, and vital signs (including body weight).

Summary tables for number and percentage of patients with adverse drug reactions (i.e., AEs related to study drug) will be tabulated.

Adverse events will be summarized by System Organ Class and preferred term, based on Medical Dictionary for Regulatory Activities coding, and grade of severity. The incidence of treatment emergent AEs will also be displayed by severity and relationship to the study drug, respectively. In addition, the incidence of AEs leading to withdrawal from treatment and SAEs will be tabulated.

Incidence of Selected AEs (see Section 5.2.4) will be tabulated. IRRs will be further analyzed according to whether they meet Sampson's criteria for diagnosis of anaphylaxis (Sampson et al, 2006).

Laboratory values (including hematology, blood chemistry, and urinalysis), frequencies of laboratory abnormalities, vital signs (temperature, SBP, DBP and pulse rate), physical examination, 12-lead ECG, and suicidality (C-SSRS) will be summarized. Measurement and change from Baseline in continuous laboratory parameters (hematology, clinical chemistry, and urinalysis), continuous ECG, vital signs (blood pressures and pulse rate), and body weight will be summarized using descriptive statistics. When analyzing categorical data, the number and percentage of patients in each category will be presented. In addition, shift tables may be used to evaluate the number and percentage of patients having a different post-baseline status when compared to their baseline status. Numbers of patients who meet the marked abnormality criteria will also be presented.

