5.11.2 Adverse Events

Adverse events will be coded using most recent version of MedDRA. All summaries will be sorted alphabetically by System Organ Class (SOC) and preferred term (PT), starting with the most frequent event. All adverse events reported in whole study will be reported in listings. For AEs, if the AE intensity is missing, the worst case (severe) will be assumed. If the drug relationship is missing, the worst case (drug related) will be assumed. In summaries, multiple occurrences of the same PT event in one individual counted only once.

The following summary tables of AEs will be provided:

- An overall summary of AEs will be presented. It will include the number and percentage of subjects with at least 1 AE, serious AE, AE leading to early discontinuation of treatment, and severe AE and number of death.
- A summary of AEs by SOC and PT.
- A summary of AEs by Intensity, SOC and PT.
- A summary of AEs leading to discontinuations of treatment.
- A summary of AEs leading to drug interruption.
- A summary of adverse drug reactions (ADRs) by SOC and PT.
- A by-subject listing of all AEs.
- A by-subject listing of all AEs leading to treatment discontinuation.
- A by-subject listing of all AEs leading to drug interruption.
- A by-subject listing of all ADRs.

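### Protocol 5.3.5.4 and 5.3.5.5 let the recorded severity of a laboratory or vital-sign AE be lowered on improvement, against 5.3.5.3, and the SAP has no maximum-intensity rule to settle the conflict

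*Protocol*

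**What the plan says.** Protocol 5.3.5.3 (persistent AEs) allows one record per event. The initial severity is entered and then "the severity should be updated to reflect the most extreme severity any time the event worsens". On seriousness it provides for one direction only: "If the event becomes serious, the Adverse Event page of the eCRF should be updated to reflect this". The section is not limited to non-laboratory events.

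Protocol 5.3.5.4 (laboratory values) says the same abnormality "should not be repeatedly recorded on the Adverse Event page of the eCRF, unless the etiology or severity changes", and goes on: "The initial severity of the event should be recorded, and the severity or seriousness should be updated any time the event worsens or improves". Protocol 5.3.5.5 (vital signs) repeats the rule: "the severity or seriousness should be updated any time the event worsens or improves".

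The grade is used in the analysis. Protocol 6.6 states: "The incidence of treatment emergent AEs will also be displayed by severity and relationship to the study drug, respectively". SAP 5.11.2 lists "A summary of AEs by Intensity, SOC and PT" and an overall summary that includes subjects with a severe AE. It counts repeat occurrences of a preferred term in one subject once, and treats a missing intensity as severe. Neither document says that the maximum intensity is used, or whether the eCRF severity field is overwritten or keeps a history.

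**The concern.** A severity table is normally read as showing the worst grade each subject reached. Under 5.3.5.3 it would. Under 5.3.5.4 and 5.3.5.5 the grade that reaches the table may instead be the one to which the event had improved. The two rules give the same result for an event that only worsens. They differ for an event that was worse and then got better.

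The point bears on this drug's safety profile. Protocol 5.1.1.2 to 5.1.1.4 single out neutrophils, platelets and liver enzymes for risk mitigation, and the protocol describes most neutrophil decreases as transient or intermittent and most transaminase elevations as resolving on treatment. These are the kinds of finding for which an improvement rule comes into play, if they are recorded as AEs and graded severe. The SAP's own convention is conservative, since an unknown intensity counts as severe. A rule that lets a documented severe grade be lowered runs against that.

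**Working it through.** No arithmetic applies, because neither document gives a count of laboratory or vital-sign AEs by severity. The check sets the recording rules beside the counting rules.

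**1. The recording rules**

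| | 5.3.5.3 (persistent AE) | 5.3.5.4 and 5.3.5.5 |
|---|---|---|
| Records per event | One | No repeat record unless etiology or severity changes |
| Severity on worsening | Raised to the most extreme | Updated |
| Severity on improvement | No change provided for | Updated |
| Seriousness | Updated if the event becomes serious | Updated on worsening or improvement |

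A laboratory AE that persists across visits falls under both columns. They conflict on severity and seriousness at improvement and, if a severity change opens a new record, on the number of records.

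**2. One event through each rule**

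Take an illustrative laboratory AE graded mild, then severe, then mild before it resolves.

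- Under 5.3.5.3 there is one record, graded severe.
- Under 5.3.5.4 with a single record updated, there is one record, graded mild. The event stays in the AE tables, in the mild column, and the subject no longer contributes to the severe-AE count through this event.
- Under 5.3.5.4 with a new record at each change, there are three records: mild, severe, mild. The severe record survives. On its natural reading the count of subjects with a severe AE is then intact. In the table by intensity, SOC and PT the preferred term is counted once and the SAP does not say at which of the two intensities.

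**3. Seriousness**

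On a single record, 5.3.5.4 would also allow seriousness to be lowered on the eCRF. Protocol 5.4.2 requires a separate paper SAE form within 24 hours, so the serious report itself is preserved. SAP 5.11.3 does not say which source the SAE tables use.

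**4. What else shows the peak**

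- SAP 5.11.4 tabulates AST and ALT by maximum post-baseline level. This covers those two tests only.
- Protocol 6.6 gives numbers of patients meeting marked-abnormality criteria, and SAP 5.11.9 gives a listing. In SAP 7.1 the lower limits are 1.50 × 10⁹/L for neutrophils (1,500/µL) and 100 × 10⁹/L for platelets (100,000/µL). These do not separate the lowest bands of protocol Tables 2 and 3 (ANC below 500/µL, platelets below 50,000/µL).
- The SAP 5.11.9 shift table uses the double-blind endpoint value, not the worst value, and the by-visit summaries leave out unscheduled visits (SAP 5.2).
- SAP 5.11.11 counts abnormal vital signs against fixed limits.
- Protocol 7.1 keeps corrections in the EDC audit trail, but neither document says the tables draw on it.

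**The case against.** The strongest reply is that the loss of the peak grade is an inference. It needs one field to be overwritten, and the sentence just before the update rule allows re-recording when severity changes. The eCRF, which would settle this, is not among the documents. That stands, and it makes the effect conditional. It does not rescue the plan, because the re-recording route leads to a table with no stated intensity rule.

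Second, protocol Table 5 grades severity by effect on daily activity, and severe means incapacitating. A very low count is not in itself a severe AE. Where the abnormality is a sign of a disease, 5.3.5.4 has only the diagnosis recorded. This stands too: few isolated laboratory AEs may ever be graded severe. The protocol's remarks on neutrophils and transaminases describe laboratory changes, and the transaminase elevations are called mild and moderate. They do not show that severe AEs were downgraded.

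Third, resolution does not oblige a site to regrade severity; protocol 5.5.1 asks only that resolution be documented with dates.

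Fourth, the double-blind period is complete, so new protocol wording cannot alter the randomised comparison. That is correct. The SAP line and the audit-trail check can still bear on it, and AE recording continues in the extension, where dosing may run to 31 December 2021.

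A reader might go further and infer that recovered severe events vanish from the severity tables, that all of them are regraded, or that one arm is favoured. The documents support none of these. The event moves to another column and stays counted. The share regraded depends on unknown site practice. A difference between arms would need more improving severe laboratory AEs in one arm, and no such figure is given.

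**Conclusion.** The contradiction between 5.3.5.3 and 5.3.5.4/5.3.5.5 is certain from the text, as is the absence of a maximum-intensity rule in the SAP. The consequence is conditional. With a single updated record, both the severe-AE count and the table by intensity can understate peak severity. With new records, only the table by intensity is left undetermined. Either way the result can depend on how each site read the instruction.

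The size cannot be stated. It depends on how many laboratory and vital-sign AEs were graded severe and then improved, and on how many of those were overwritten. The first number may be small. The separate laboratory displays and the SAE form limit the harm to interpretation, but they do not replace a correct severity table, least of all for non-serious severe events outside AST and ALT.

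The disputed sentences are not in the italics that mark text new in Version 11. I therefore assume, without having seen the earlier versions, that they also governed the double-blind period.

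**What to change.** - **Protocol 5.3.5.4 and 5.3.5.5:** replace the update sentence with the 5.3.5.3 rule. Severity is raised to the most extreme grade when the event worsens, and neither severity nor seriousness is lowered on improvement, which is shown by outcome and end date. Tell sites by memo.
- **SAP 5.11.2:** state that intensity summaries use the maximum recorded intensity per subject and preferred term.
- **Data already entered, including the double-blind period:** search the EDC audit trail for laboratory and vital-sign AEs whose severity or seriousness was lowered, and restore or report the peak grade.

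The cost is one sentence in each of two protocol sections, one SAP line, a memo and a small one-off check. Severe-AE counts may become slightly less favourable. The change affects recording and counting only and alters no treatment rule.
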